2.2. Objectives and secondary endpoints

2.2.1. Secondary objective(s)

1. Assessing the impact of anti-slip socks on short-term motor skills
2. Evaluate the impact of anti-slip socks on motor planning in the short term and during hospitalization
3. Evaluate the impact of wearing socks on dual-task abilities in the short term and during hospitalization
4. Evaluate the evolution of fear of falling with the use of socks in the short term and during hospitalization.
5. Evaluate the impact of socks on the presence of fall(s)
6. Length of stay in geriatric care or post-emergency medicine

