2.2.2. Secondary endpoints

1. Change in 10m walking speed between D1 (start of physiotherapy treatment) and D1' ("after a 3-minute walk with the shoe assigned following randomization"),
2. Evolution of isochrony between the speed of walking actually performed and the speed of walking imagined over 10m at D1, D1' and D8. The mean of two tests of each modality will be used.
3. Evolution of isochrony between walking speed and double-task walking speed over 10m at D1,D1' and D8 (Beauchet et al., 2010; Menant et al., 2014). The mean of two tests of each modality will be used.
4. Total score > 10 on the Short-Falls Efficacy Scale International questionnaire at D1, D1' and D8
5. Presence of fall(s) and their consequences during hospitalization
6. Length of stay calculated from start of hospitalization to end of hospitalization

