3.2. Inclusion criteria

- Patient in Geriatric Short Stay or Post-Emergency Medicine,
- Patient aged 75 and over,
- Patient requiring physiotherapy,
- Patient with at least 7 days of physiotherapy treatment
- Patient arrives with unsuitable footwear (assessment at clinician's discretion: no back support, unsuitable size, etc.) or no footwear at all,
- Patient able to walk at least 10 m with or without technical aids,
- Patient with oral consent
- Patient with social security coverage.

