4. DESIGN AND STUDY PROCESS

4.1. Study schedule

4.1.1. Inclusion and baseline tests (J1)

Patients arrive on the ward and are assessed by the doctor, who prescribes physiotherapy if necessary.

The physiotherapist takes note of the prescription on the first working day thereafter. The physiotherapist carries out a routine analysis of the patient's footwear. If the footwear is unsuitable, or if the patient is barefoot, the physiotherapist checks the patient's eligibility criteria. If the patient meets these criteria, he or she is informed of the study. If the patient gives oral consent, the physiotherapist will perform the Baseline tests (D1).

Baseline: J1 tests

The physiotherapist assesses the patient during the first diagnostic session, and performs the *Confusion Assessment Method* if it has not been done in routine practice.

A Visual Analogue Fatigue Assessment will be carried out prior to clinical testing.

For research purposes, the J1 tests will be performed barefoot:

1. Patient's walking speed over 10 m (2 times)
2. Walking speed in dual-task situation over 10 m (2 times)

Two other less common but validated assessments in this population will be carried out.

3. Imagined walking speed over 10 m (2 times)

The average of each of the two tests will be used for items 1 to 4.

Together, these tests take the patient around 10 minutes.

4. Short-Falls Efficacy Scale International Questionnaire

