4.5.7. Length of stay

The length of stay in days and hours in geriatric short-stay or post-emergency medicine, calculated between the start of hospitalization and the end of hospitalization, will be recorded.

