6.2.1. Description of planned statistical methods, including schedule of planned interim analyses

All variables will be described globally and by group. The description will include the number and percentage of modalities for qualitative variables, and the minimum, maximum, mean, standard deviation and median for quantitative variables.

All gait speed criteria, isochrony between imagined and executed gait speed, isochrony between normal gait speed and double-task gait will be compared using linear models taking into account the baseline J1 value.

As the evaluation conditions between D1' and D8 are different, the models evaluating evolution at D1' and D8 will be independent.

Fear of falling will be assessed using the Falls Efficacy Scale International questionnaire. Fear of falling is defined with a cut-off score equal to 10 on this questionnaire.

The number and percentage of patients with a fear of falling will be presented and compared at D1' and D8 using a Chi2 test.

Length of stay will be compared using a Student's t test.

The presence of falls and their consequences will be described during the hospital stay.

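### Length of stay is counted from before randomisation and compared without adjustment, which usually costs some precision but does not bias the comparison

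*Combined protocol and SAP*

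**What the plan says.** Section 2.2.2 defines endpoint 6 as "Length of stay calculated from start of hospitalization to end of hospitalization". Section 4.5.7 uses the same clock: the stay in geriatric short-stay or post-emergency medicine, in days and hours, is "calculated between the start of hospitalization and the end of hospitalization". The matching objective in section 2.2.1 is "Length of stay in geriatric care or post-emergency medicine".

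Section 4.1.1 sets out what happens before D1: "Patients arrive on the ward and are assessed by the doctor, who prescribes physiotherapy if necessary". Then, "The physiotherapist takes note of the prescription on the first working day thereafter". The footwear check, the eligibility check, information and oral consent follow. Randomisation is on D1 and allocated footwear is first worn after it (section 4.1.2).

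For the analysis, section 6.2.1 says: "Length of stay will be compared using a Student's t test". Section 6.2.8 states that randomisation is 1:1, in blocks and unstratified. Nowhere does the plan count stay from randomisation or adjust for the days before it.

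**The concern.** The endpoint is the sum of two parts: time before allocation, which socks cannot change, and time after it, which they might. The first part varies between patients with the weekday of the prescription and with how long the prescription takes. That variation goes into the standard error of the comparison and carries no information about treatment.

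The plan treats its other main comparisons differently. The primary endpoint starts at D1, and the gait-speed and isochrony models take the D1 value into account. Length of stay is compared with neither protection.

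What is at stake is precision, with about 25 patients per arm, on an endpoint the protocol cares about: section 1.2.1.2 lists a shorter stay, and through it lower cost, as a collective benefit.

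**Working it through.** **Plan's own figure.** The documents give no mean, SD or target difference for length of stay. The only sample-size figure concerns walking speed (section 6.2.2): a difference of 0.10 m/s and an SD of 0.10, 5% alpha (taken as two-sided) and 90% power. The two-sample t calculation gives 22.02 per arm, rounded up to 23, so 46 in total. The stated figure reproduces, but it has no bearing on length of stay.

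**Inputs from the documents.** 50 randomised 1:1, so 25 per arm; no stratification; unadjusted t test; clock starting before D1.

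**Assumed inputs.** SD of post-randomisation stay, σ = 5 days. SD of pre-randomisation stay, s = 0.7 to 3 days. Correlation between them, ρ = 0 unless stated.

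**Step 1: is there bias?** Write T = A + B, where A is time from entry to randomisation and B is time from randomisation to discharge. A is fixed before allocation, so its expected value is the same in both arms. The expected between-arm difference in T therefore equals that in B. There is no bias.

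**Step 2: variance.** Var(T) = σ² + s² + 2ρsσ. With ρ = 0, the ratio to Var(B) is 1 + s²/σ². The equivalent number of patients is 50 divided by that ratio. The standard error of the chance difference in mean A is s × √(2/25).

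**Step 3: a low-end value for s.** Suppose the prescription is written on the day of arrival, arrivals are uniform over the week, and the physiotherapist acts on the next working day. The gap is 1 day for Sunday to Thursday arrivals, 3 for Friday and 2 for Saturday. The mean is 10/7 = 1.43, the mean square is 18/7 = 2.57 and the variance is 2.57 − 2.04 = 0.53, so s is about 0.73 day. Later or more variable prescriptions would raise it.

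**Step 4: results with σ = 5, ρ = 0.**

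| s (days) | variance ratio | equivalent patients of 50 | SE of chance difference in A (days) |
|---|---|---|---|
| 0.73 | 1.02 | 49 | 0.21 |
| 1 | 1.04 | 48 | 0.28 |
| 2 | 1.16 | 43 | 0.57 |
| 3 | 1.36 | 37 | 0.85 |

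For an effect that would have 80% power when stay is counted from randomisation, power when it is counted from entry is 78.4%, 73.9% and 67.1% at s = 1, 2 and 3. With σ = 7 and s = 3 the variance ratio is 1 + 9/49 = 1.18, or about 42 patients.

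**Step 5: the last two result columns show one effect.** At s = 3, the standard error of the comparison is 5 × √(2/25) = 1.41 days counted from randomisation and 5.83 × √(2/25) = 1.65 days counted from entry. Since 1.41² + 0.85² = 1.65², the chance imbalance in A is already inside the t test's standard error. It is not a second harm.

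**Step 6: correlation.** At σ = 5 and s = 3, the variance ratio is 1.72 with ρ = +0.3 and 1.00 with ρ = −0.3. At s = 1 the corresponding ratios are 1.16 and 0.92. Counting from entry is less precise only if ρ is above −s/(2σ), which is −0.3 at s = 3 and −0.1 at s = 1.

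**Step 7: adjustment.** In a linear model with arm and A as covariates, the estimated arm effect is identical for T and for B, because they differ only by A. The residual variance relative to Var(B) is 1 − ρ². The unadjusted ratio for T exceeds this by (ρ + s/σ)², which is never negative, and the unadjusted ratio for B exceeds it by ρ². Apart from one degree of freedom, the adjusted analysis is at least as precise as either unadjusted one whatever the sign of ρ.

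**The case against.** The best defence is that nothing here is invalid. The t test keeps its type I error and estimates the right difference. Total ward stay is also the natural quantity for the cost argument in section 1.2.1.2. Both points stand. Counting from entry is a defensible choice, and the gain from changing it may be trivial: section 4.1.1 describes a short path, and if the gap is little more than the wait for a working day, the variance rises by about 2%. A clearly negative correlation could even make the planned version the more precise of the two unadjusted ones.

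A reader might infer more than the documents support:

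- *That a chance imbalance in pre-randomisation days would pass for a sock effect.* The t test already allows for it (step 5).
- *That emergency-department time is counted.* Sections 2.2.1 and 4.5.7 tie the stay to the geriatric or post-emergency ward, so the clock may start at ward entry. Either reading precedes randomisation, but the plan should say which applies.
- *That the inclusion criterion "Patient with at least 7 days of physiotherapy treatment" makes matters worse by leaving socks only the period after D8 in which to act.* The criterion does not say those days run from D1. Even if they did, the minimum would remain when stay is counted from randomisation, so it does not bear on the choice of clock.
- *That the change is free because the dates are already collected.* The schedule and section 4.5.7 list length of stay as the recorded item. They do not state that entry and discharge dates are held.

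**Conclusion.** The point holds as a minor matter of precision. Endpoint 6 includes time that allocation cannot affect, and the planned analysis does nothing to remove its variance. There is no bias and no threat to the validity of the test.

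The size cannot be established from the documents. On the assumptions above (post-randomisation SD 5 days, independent pre-randomisation SD 0.7 to 3 days) the loss runs from about 1 to about 13 of the 50 patients. The upper end depends wholly on the assumed 3-day SD. A positive correlation would enlarge the loss, and a clearly negative one could cancel or reverse it.

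Sections 4.1.2 and 6.2.8 disagree on whether randomisation comes after or before the D1 tests. They should be reconciled, but on either version randomisation follows entry, so the conclusion is unchanged.

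**What to change.** - In sections 2.2.2 and 4.5.7, define the compared endpoint as time from randomisation (D1) to discharge from the geriatric short-stay or post-emergency ward.
- In section 6.2.1, replace the t test for this endpoint with a linear model containing arm and days from ward entry to D1. This is the same kind of model already planned for gait speed, and it protects against either sign of correlation.
- Report days from ward entry to D1 by arm as a baseline characteristic. Keep total stay as a descriptive figure for the cost discussion, and state whether it starts at hospital or ward entry.

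The cost is about one sentence in each of the three sections. The eCRF must hold the entry, randomisation and discharge dates. Randomisation is done electronically (section 6.2.8), so its date should be available; the other two need to be confirmed. The compared stay will be shorter than the administrative stay, which the report should explain. The primary endpoint and the sample size do not change.

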3. STUDY POPULATION

3.1. Description of the population

This study is aimed at patients admitted to the CHD Vendée in Post-Emergency Medicine and Geriatric Short Stay who require physiotherapy treatment.

3.2. Inclusion criteria

- Patient in Geriatric Short Stay or Post-Emergency Medicine,
- Patient aged 75 and over,
- Patient requiring physiotherapy,
- Patient with at least 7 days of physiotherapy treatment
- Patient arrives with unsuitable footwear (assessment at clinician's discretion: no back support, unsuitable size, etc.) or no footwear at all,
- Patient able to walk at least 10 m with or without technical aids,
- Patient with oral consent
- Patient with social security coverage.

3.3. Non-inclusion criteria

- Inability to understand or perform clinical tests specific to the study
- Known cognitive impairment, disease or condition that compromises comprehension of information or informed consent by the patient
- Blind patient
- Patients under guardianship or trusteeship
- Patient participating in an interventional clinical research protocol likely to modify the assessments of the present protocol.
- Patient previously included in the Charm study
- Patient with identified risk of being unable to wear socks or go barefoot within the next 7 days (need for compression stockings or socks, wound, excessive edema, orthostatic hypotension, other).

The investigator/qualified person, or a person designated by the investigator/qualified person, must keep an up-to-date list of patients not included throughout the study. This list should include all patients from the population who do not meet the eligibility criteria. The list should also indicate, for each patient, the reason for non-inclusion in the study.

4. DESIGN AND STUDY PROCESS

4.1. Study schedule

4.1.1. Inclusion and baseline tests (J1)

Patients arrive on the ward and are assessed by the doctor, who prescribes physiotherapy if necessary.

The physiotherapist takes note of the prescription on the first working day thereafter. The physiotherapist carries out a routine analysis of the patient's footwear. If the footwear is unsuitable, or if the patient is barefoot, the physiotherapist checks the patient's eligibility criteria. If the patient meets these criteria, he or she is informed of the study. If the patient gives oral consent, the physiotherapist will perform the Baseline tests (D1).

Baseline: J1 tests

The physiotherapist assesses the patient during the first diagnostic session, and performs the *Confusion Assessment Method* if it has not been done in routine practice.

A Visual Analogue Fatigue Assessment will be carried out prior to clinical testing.

For research purposes, the J1 tests will be performed barefoot:

1. Patient's walking speed over 10 m (2 times)
2. Walking speed in dual-task situation over 10 m (2 times)

Two other less common but validated assessments in this population will be carried out.

3. Imagined walking speed over 10 m (2 times)

The average of each of the two tests will be used for items 1 to 4.

Together, these tests take the patient around 10 minutes.

4. Short-Falls Efficacy Scale International Questionnaire

4.1.2. Randomization

Once the tests have been carried out, randomization will be carried out by the physiotherapist.

Randomization arm :

- Control arm: usual care with bare feet.
- Experimental arm: specific management with non-slip socks.

Depending on the randomization arm, the physiotherapist will put non-slip socks on patients in the experimental arm and leave patients in the control arm barefoot. He will then encourage the patient to walk for 3 minutes.

4.1.3. J1' follow-up

After these 3 minutes of walking with or without the socks, depending on the randomization arm, and in order to assess the immediate effect of wearing anti-slip socks on motor skills, the patient will perform the same tests as on D1, in the same order.

A Visual Analogue Fatigue Assessment will be performed prior to the following clinical tests:

1. Patient's walking speed over 10 m (2 times)
2. Walking speed in dual-task situation over 10 m (2 times)
3. Imagined walking speed over 10 m (2 times)

The tests will be carried out by the patient with bare feet (control arm) or with non-slip socks (experimental arm).

4.1.4. Patient care procedures during the stay

Following this second evaluation and for the duration of hospitalization, socks will be left on patients in the experimental arm, and patients in the control arm will remain barefoot. A notice will be posted in the patients' rooms to inform the nursing teams so that the randomization arm is respected.

Between D1' and D8, the patient will undergo rehabilitation according to a pre-established plan based on the conclusions of the BDMK. The patient will benefit from 3 sessions, the first of which includes the assessment on D1.

4.1.5. Follow-up J8

At D8, in order to assess the effect of socks on motor preservation/recovery, the patient will be reassessed under the same conditions as at D1, i.e. barefoot, using the same tests as at D1 and in the same order.

A Visual Analogue Fatigue Assessment will be performed prior to the following clinical tests:

1. Patient's walking speed over 10 m (2 times)
2. Walking speed in dual-task situation over 10 m (2 times)
3. Imagined walking speed over 10 m (2 times)
4. Short-Falls Efficacy Scale International Questionnaire

Study schedule

Actions	J1	J1' (after 3 minutes of free walking)	J8	Hospital discharge
Patient information	X			
Informed Consent	X			
Checking inclusion and non-inclusion criteria	X			
Randomization	X			
Confusion Assessment Method	X			
EVA fatigue	X	X	X	
History (falls, MMSE, etc.)	X			
Type of technical aid	X	X	X	
Clinical examination	X		X	
Tests :				
• Walking speed at patient's preferred speed over 10m (x2),				
• Double-task walking speed over 10m (x2),	X	X	X	
• Imagined walking speed over 10m (x2),				
Short-FESI questionnaire	X		X	
Length of stay in geriatric care or post-emergency medicine				X

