1.2. Benefits and risks for research subjects

1.2.1. Benefits

1.2.1.1. *Individual profit*

Improved motor control
Improved practices with the use of non-slip socks

1.2.1.2. *Group profit*

Improved motor care for senior citizens, at a lower cost to society thanks to a shorter length of stay,
Improved motor management for faster discharge

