2.1.2. Primary endpoint

Evolution of walking speed at the patient's preferred speed over 10m between D1 (start of physiotherapy treatment) and D8. Two tests will be performed at each assessment, and the average of the two tests will be used.

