4.2. General research methodology

The research has the following characteristics:

- Open study,
- Monocentric (CHD Vendée)
- Controlled,
- Superiority,
- Randomized

[figure not shown]
Inclusion period: 18 months

Participation period: 7 days

Research duration: 19 months maximum

Number of patients to be randomized: 50

4.3. *Study diagram*

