4.6. Identification of all source data not contained in the medical record

1. Confusion Assesment Method scale	at D1
2. Visual Analogue Fatigue Scale	at D1, D1' and D8
3. Type of technical aid(s)	at J1, J1', J8
4. Duration of 10 m walk (2 times) performed	at D1, D1' and D8
5. Duration of double-task 10 m walk (2 times) performed	at D1, D1' and D8
6. Duration of imagined 10 m walk (2 times) performed	at D1, D1' and D8
7. Short-Falls Efficacy Scale International questionnaire	at D1, D1' and D8

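### No walking test is planned for a patient discharged before D8, so that patient enters the primary analysis with an imputed zero recovery instead of a measured value

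*Combined protocol and SAP*

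**What the plan says.** The primary endpoint (2.1.2) is "Evolution of walking speed at the patient's preferred speed over 10m between D1 (start of physiotherapy treatment) and D8". The follow-up that supplies it is described in 4.1.5: at D8, "the patient will be reassessed under the same conditions as at D1, i.e. barefoot, using the same tests as at D1".

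The schedule in 4.1.5 marks the walking tests at J1, J1' and J8. The source-data list in 4.6 agrees: the entry "Duration of 10 m walk (2 times) performed" is given for D1, D1' and D8. The schedule also has a hospital-discharge column, but the only row marked there is "Length of stay in geriatric care or post-emergency medicine". No section gives a window around D8, a return visit, or a test before an early discharge. The study diagram in 4.3 is not visible in the text, but the two lists are consistent with each other.

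Two entries bear on who reaches D8. Section 3.2 requires "Patient with at least 7 days of physiotherapy treatment", and 4.2 gives "Participation period: 7 days". Section 4.7.1 names withdrawal of consent and death as reasons for ending participation; early discharge is not among them.

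On analysis, the main population is all randomized patients (6.2.7). A missing D8 value for the primary endpoint is replaced by the patient's D1 value, with multiple imputation as a sensitivity analysis only if more than 10% are missing (6.2.5).

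**The concern.** D1' cannot stand in for D8. It follows a 3-minute walk directly after allocation and is performed in the assigned footwear (4.1.3), so it measures an immediate effect under different conditions. That leaves one usable follow-up, on short-stay and post-emergency wards, with no rule for a patient who goes home first. Such a patient is not withdrawn under 4.7.1, remains in the ITT set, and is scored as not having changed.

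The 7-day physiotherapy criterion is the only protection. Eligibility is checked at D1, and D1 is by definition the start of physiotherapy, so the criterion can only be a forecast.

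The loss may also be informative. Section 1.2.1 lists "Improved motor management for faster discharge" among the expected benefits, and length of stay is a secondary endpoint. If patients leave because they have recovered, the imputed zero falls on those with a real gain. If socks shorten the stay, it falls more often on the socks arm. The D8 isochrony and Short-FES-I values are lost for the same patients, and 6.2.5 gives an imputation rule for the primary endpoint only.

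**Working it through.** **The plan's own figure.** Inputs from 6.2.2: difference 0.10 m/s, SD 0.10, alpha 5%, power 90%, 1:1 allocation. Sidedness is not stated. The two-sided normal approximation gives 22 per arm, 44 in total. The two-sided t-test gives power 0.8997 at 22 per arm and 0.912 at 23 per arm, hence 46 in total, as stated. A one-sided test gives 36 and does not match. With 25 per arm and every D8 value measured, power is 93.4%. The margin from 46 to 50 is 4/50 = 8%; no dropout rate is stated.

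**Assumptions not in the documents.** A share m of each arm leaves before D8 (10, 20 or 30%); early leavers have the average recovery of their arm; gain is linear over the 7 days from D1 to D8; discharge is on D6 (5 of 7 days elapsed) or D3 (2 of 7).

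**Expected difference, equal m in both arms**

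- Current plan, D1 value imputed: 0.10 × (1 − m)
- Test on D6: 0.10 × [(1 − m) + m × 5/7] = 0.10 × (1 − 2m/7)
- Test on D3: 0.10 × [(1 − m) + m × 2/7] = 0.10 × (1 − 5m/7)

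| m | Current plan | Test on D6 | Test on D3 |
|---|---|---|---|
| 10% | 0.090 | 0.097 | 0.093 |
| 20% | 0.080 | 0.094 | 0.086 |
| 30% | 0.070 | 0.091 | 0.079 |

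At m = 20% the test recovers 0.094 − 0.080 = 0.014 m/s for discharge on D6, but only 0.086 − 0.080 = 0.006 m/s for D3.

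**Power, 25 per arm.** Under imputation, an arm with mean change μ has variance (1 − m) × 0.10² + m(1 − m) × μ². For m = 10, 20, 30%, power is 89, 84, 77% if the control arm's mean change is 0, and 87, 79, 70% if it is 0.05 m/s. With a pre-discharge test that carries half of the D8 change, it is 90–91, 86–87 and 81–83%. D6 corresponds to a fraction of 5/7 = 0.71, better than that row; D3 to 2/7 = 0.29, worse.

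**Unequal loss.** Assume a control gain of 0.05 and a socks gain of 0.15 m/s.

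- 10% of controls and 30% of socks patients leave early: 0.70 × 0.15 − 0.90 × 0.05 = 0.105 − 0.045 = 0.060 m/s, power 53%.
- The same with a test on D6: 0.15 × (0.70 + 0.30 × 5/7) − 0.05 × (0.90 + 0.10 × 5/7) = 0.137 − 0.049 = 0.089 m/s after rounding.
- Shares reversed (30% control, 10% socks), no test: 0.90 × 0.15 − 0.70 × 0.05 = 0.135 − 0.035 = 0.100 m/s, no shrinkage.

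The direction and size therefore depend on who leaves.

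**The case against.** The entry criterion already selects against early leavers and matches the participation period. Any such criterion applied at D1 is a forecast, so early discharge may be rare. At m = 10% the current plan still has 87–89% power, close to the planned 90%. This stands: the documents give no rate, and the gap may affect few patients.

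The shrinkage is also a product of the imputation rule in 6.2.5. If the leavers resembled the others and were simply left out, the difference would stay at 0.10 m/s, with 87% power at m = 20% (20 per arm). This stands too, and the same loss should not be counted again in any comment on the imputation. What remains is that no rule can test whether the leavers resemble the others when their speed was never taken.

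A discharge-day value is not a D8 value. If socks shorten the stay, socks patients would be measured earlier, which brings a timing difference between arms. That is a true cost of the remedy, which is why it needs an analysis rule as well as an extra visit.

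Two stronger readings are tempting. A reader might infer that an early leaver has no primary outcome at all; the plan does assign one, by imputation, and what is missing is a measured follow-up. A reader might also infer that those who miss D8 are the fastest recoverers, mostly in the socks arm. Section 1.2.1 states a general expected benefit and says nothing about who leaves before D8, so that link is possible but not shown.

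**Conclusion.** The gap is real: the plan has no measured follow-up for a patient discharged before D8 and scores that patient as unchanged. Its size cannot be fixed from the documents. For an assumed equal share of 10–30%, the planned 0.10 m/s would be diluted to 0.090–0.070 under the imputation rule in 6.2.5. A test before discharge would bring it back to 0.097–0.091 if discharge is on D6, and only to 0.093–0.079 if on D3. These figures rest on linear gain and on leavers having their arm's average recovery. The 53% power in the unequal example shows what is possible, not what is expected.

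The documents do not support a claim that the result will be biased in a known direction, nor that an early discharge would be treated afterwards as an eligibility violation. The change is worth making because it is cheap and replaces an assumption with a measurement; the trial does not fail without it.

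**What to change.** - **4.1.5 and the schedule:** add that, if discharge is planned before D8, the J8 battery (barefoot, same order) is performed on the day of discharge or the last working day before it, with the date recorded. Mark the walking tests, fatigue scale and Short-FES-I in the hospital-discharge column for these patients.
- **2.1.2 and 6.2.5:** state that the primary analysis uses the last barefoot value measured on the ward after D1 and up to D8, in place of the imputed D1 value. Exclude D1' explicitly, since it is barefoot in the control arm only. Where no such value exists, the present rule in 6.2.5 continues to apply.
- **6.2:** add a sensitivity analysis restricted to values measured at D8, and report the day of assessment by arm.
- **3.2:** wording the criterion as an expected duration of physiotherapy would be clarification only.

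The cost is protocol wording, one eCRF date and about 10 minutes per early leaver (the test duration given in 4.1.1), with no new test. The downside is that some values cover fewer than 7 days, possibly unequally between arms; the D8-only analysis and the report of assessment days make this visible.
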